## Statistical Analysis Plan (RotW)

Final v1.0, 08FEB2022

SG018

	discharge after Day 28 would not be appropriate. Premature study withdrawal is expected to be independent to the treatment effect, therefore a censoring approach in this scenario is considered appropriate.
Other protocol deviations affecting efficacy	Hypothetical (estimand for a situation with no protocol deviations affecting efficacy): To establish the true treatment effect the time to hospital discharge will be considered missing if protocol deviations affecting efficacy are recorded on or prior to Day 35.
Medications affecting efficacy	Treatment policy: Time to hospital discharge will be used regardless of any concomitant medication use.

A second supportive estimand will estimate the hazard ratio of SNG001 versus placebo for the time to hospital discharge of patients in the per protocol population who do not receive medications affecting efficacy. Medications affecting efficacy will be defined as COVID-19 therapies which are approved for use (including emergency use) at the time of the primary analysis and will be handled as per table 10.

**Table 10: Intercurrent events and policies for the second supportive estimand of time to hospital discharge**

Intercurrent event	Policy
Death	Composite variable: Patients who die during the study period will have time to hospital discharge right censored at 28 days (the maximum time to discharge).
Missed 2 of the first 3 scheduled doses	Hypothetical (estimand for a situation with treatment compliance): The time to hospital discharge will be considered missing if two or more doses of the randomised treatment were missed within the first three days of therapy, with the corresponding patients excluded from the PP analysis set. A single dose within the first three scheduled dosing days is not expected to be sufficient for the study drug to be effective, therefore this approach will help establish the true treatment effect. It is assumed that such exclusions are not related to treatment.
Other premature treatment discontinuation and missed doses	Treatment policy: The time to hospital discharge will be used regardless of treatment discontinuation and the number of missed doses (other than missing 2 out of the first 3 scheduled doses).
Withdrawal from study following hospital discharge	Hypothetical: The time to hospital discharge will be used regardless of study withdrawal where discharge was sustained for 7 days. Otherwise patients will be censored at the last date known to be hospitalised for patients who withdrew during the 7 day rebound period. This approach has been proposed because discontinuation during the rebound period is expected to be due to lack of interest/lack of motivation/lack of time to continue participating in the study rather than relapse.

## Statistical Analysis Plan (RotW)

Final v1.0, 08FEB2022

SG018

Withdrawal from study prior to hospital discharge	While-on-study: Time to hospital discharge will be right censored at the time of withdrawal from the study or at 28 days, whichever occurs first. The evaluation period for this endpoint is 28 days, therefore estimating the time to hospital discharge after Day 28 would not be appropriate. Premature study withdrawal is expected to be independent to the treatment effect, therefore a censoring approach in this scenario is considered appropriate.
Other protocol deviations and prior medications affecting efficacy	Hypothetical (estimand for a situation with no protocol deviations or prior medications affecting efficacy): To establish the true treatment effect the time to hospital discharge will be considered missing if protocol deviations affecting efficacy are recorded on or prior to Day 35 or medications affecting efficacy are being received at the time of first dose.
Concomitant medications affecting efficacy	Composite: If approved COVID-19 treatments are given the patients receiving them will be right censored at date prior to first medication use.

**9.1.1.5 Analysis of the Supportive Estimands**

The supportive estimand of the time to hospital discharge primary endpoint will be analysed using the same methods as the primary estimand, as detailed in [Section 9.1.1.2](#).

**9.1.2 Time to Recovery****9.1.2.1 Primary Estimand**

The second primary estimand will be the hazard ratio of SNG001 versus placebo for the time to recovery of patients in the ITT population. Intercurrent events will be handled as per table 11.

**Table 11: Intercurrent events and policies for the primary estimand of time to recovery**

Intercurrent event	Policy
Death	Composite variable: Patients who die during the study period will have time to recovery right censored at 28 days (the maximum possible time to recovery).
Premature treatment discontinuation and missed doses	Treatment policy: The time to recovery will be used regardless of treatment discontinuation and the number of missed doses.
Withdrawal from study following recovery	Hypothetical: The time to recovery will be used regardless of study withdrawal where recovery was sustained for 7 days Otherwise patients will be censored at the last date known to have limitation of activities for patients who withdrew during the 7 day rebound period. This approach has been proposed because discontinuation during the rebound period is expected to be due to lack of interest/lack of motivation/lack of time to continue participating in the study rather than relapse.

## Statistical Analysis Plan (RotW)

Final v1.0, 08FEB2022

SG018

Withdrawal from study prior to recovery	While-on-study: Time to recovery will be right censored at the time of withdrawal from the study or at 28 days, whichever occurs first. The evaluation period for this endpoint is 28 days, therefore estimating the time to recovery after Day 28 would not be appropriate. Premature study withdrawal is expected to be independent to the treatment effect, therefore a censoring approach in this scenario is considered appropriate. However, this assumption will be tested by appropriate sensitivity analyses.
Other protocol deviations and concomitant medications affecting efficacy	Treatment policy: Time to recovery will be used regardless of any concomitant medication use or protocol deviations.

**9.1.2.2 Analysis of the Primary Estimand**

Time to recovery will be analysed using the same methods as time to hospital discharge, as detailed in [Section 9.1.1.2](#).

**9.1.2.3 Sensitivity Analyses of the Primary Estimand**

The sensitivity to missing data will be assessed in the same way as described for time to hospital discharge in [Section 9.1.1.3](#).

The primary estimand will be further evaluated for each of the subgroups described in [Section 7.2](#). The analysis method for time to hospital discharge described in [Section 9.1.1.2](#) will be used to evaluate each subgroup.

**9.1.2.4 Supportive Estimands**

A supportive estimand of the primary endpoint will estimate the hazard ratio of SNG001 versus placebo for the time to recovery of patients in the per protocol population. Reasons for excluding patients from the PP population are described in [Section 7.1.2](#). Of note, many of the reasons are based on assessments prior to randomisation and treatment and so the exclusions are independent of treatment. Intercurrent events will be handled as per table 12.

**Table 12: Intercurrent events and policies for the supportive estimand of time to recovery**

## Statistical Analysis Plan (RotW)

Final v1.0, 08FEB2022

SG018

Intercurrent event	Policy
Death	Treatment policy: Patients who die during the study period will have time to recovery right censored at 28 days (the maximum possible time to recovery).
Missed 2 of the first 3 scheduled doses	Hypothetical (estimand for a situation with treatment compliance): The time to recovery will be considered missing if two or more doses of the randomised treatment were missed within the first three days of therapy, with the corresponding patients excluded from the PP analysis set. A single dose within the first three scheduled dosing days is not expected to be sufficient for the study drug to be effective, therefore this approach will help establish the true treatment effect. It is assumed that such exclusions are not related to treatment.
Other premature treatment discontinuation and missed doses	Treatment policy: The time to recovery will be used regardless of treatment discontinuation and the number of missed doses (other than missing 2 out of the first 3 scheduled doses).
Withdrawal from study following recovery	Hypothetical: The time to recovery will be used regardless of study withdrawal where recovery was sustained for 7 days Otherwise patients will be censored at the last date known to have limitation of activities for patients who withdrew during the 7 day rebound period. This approach has been proposed because discontinuation during the rebound period is expected to be due to lack of interest/lack of motivation/lack of time to continue participating in the study rather than relapse.
Withdrawal from study prior to recovery	While-on-study: Time to recovery will be right censored at the time of withdrawal from the study or at 28 days, whichever occurs first. The evaluation period for this endpoint is 28 days, therefore estimating the time to recovery after Day 28 would not be appropriate. Premature study withdrawal is expected to be independent to the treatment effect, therefore a censoring approach in this scenario is considered appropriate.
Other protocol deviations affecting efficacy	Hypothetical (estimand for a situation with no deviations affecting efficacy): To establish the true treatment effect the time to recovery will be considered missing if protocol deviations affecting efficacy are recorded on or prior to Day 35.
Medications affecting efficacy	Treatment policy: Time to recovery will be used regardless of any concomitant medication use.

A second supportive estimand will estimate the hazard ratio of SNG001 versus placebo for the time to recovery of patients in the per protocol population who do not receive medications affecting efficacy. Medications affecting efficacy will be defined as COVID-19 therapies which are approved for use (including emergency use) at the time of the primary analysis and will be handled as per table 13.

**Table 13: Intercurrent events and policies for the second supportive estimand of time to recovery**

Intercurrent event	Policy
Death	Treatment policy: Patients who die during the study period will have time to recovery right censored at 28 days (the maximum possible time to recovery).
Missed 2 of the first 3 scheduled doses	Hypothetical (estimand for a situation with treatment compliance): The time to recovery will be considered missing if two or more doses of the randomised treatment were missed within the first three days of therapy, with the corresponding patients excluded from the PP analysis set. A single dose within the first three scheduled dosing days is not expected to be sufficient for the study drug to be effective, therefore this approach will help establish the true treatment effect. It is assumed that such exclusions are not related to treatment.
Other premature treatment discontinuation and missed doses	Treatment policy: The time to recovery will be used regardless of treatment discontinuation and the number of missed doses (other than missing 2 out of the first 3 scheduled doses).
Withdrawal from study following recovery	Hypothetical: The time to recovery will be used regardless of study withdrawal where recovery was sustained for 7 days Otherwise patients will be censored at the last date known to have limitation of activities for patients who withdrew during the 7 day rebound period. This approach has been proposed because discontinuation during the rebound period is expected to be due to lack of interest/lack of motivation/lack of time to continue participating in the study rather than relapse.
Withdrawal from study prior to recovery	While-on-study: Time to recovery will be right censored at the time of withdrawal from the study or at 28 days, whichever occurs first. The evaluation period for this endpoint is 28 days, therefore estimating the time to recovery after Day 28 would not be appropriate. Premature study withdrawal is expected to be independent to the treatment effect, therefore a censoring approach in this scenario is considered appropriate.
Other protocol deviations and prior medications affecting efficacy	Hypothetical (estimand for a situation with no protocol deviations or prior medications affecting efficacy): To establish the true treatment effect the time to recovery will be considered missing if protocol deviations affecting efficacy are recorded on or prior to Day 35 or medications affecting efficacy are being received at the time of first dose.
Concomitant medications affecting efficacy	Composite: If approved COVID-19 treatments are given the patients receiving them will be right censored at date prior to first medication use.

**9.1.2.5 Analysis of the Supportive Estimands**

The supportive estimand of the time to recovery primary endpoint will be analysed using the same methods as the primary estimand for hospital discharge, as detailed in [Section 9.1.1.2](#).

**9.2 Key Secondary Endpoints****9.2.1 Progression to Severe Disease or Death****9.2.1.1 Key Secondary Estimand**

The key secondary estimand will be the difference in probabilities for SNG001 versus placebo for progression to severe disease or death within 35 days of first dose of patients in the ITT population. Intercurrent events will be handled as per Table 14.

**Table 14: Intercurrent events and policies for the key secondary estimand of progression to severe disease or death**

Intercurrent event	Policy
Death	Composite variable: The definition of the endpoint includes patients who die within 35 days of first dose, regardless of their OSCI assessments.
Premature treatment discontinuation and missed doses	Treatment policy: Severe disease will be determined regardless of treatment discontinuation and the number of missed doses.
Withdrawal from study	While-on-study: Patients will only be considered having severe disease if observed and recorded whilst participating in the study. This assumes the treatment effect is independent to reason for study withdrawal.
Other protocol deviations and concomitant medications affecting efficacy	Treatment policy: Severe disease will be determined regardless of any concomitant medication use or protocol deviations.

**9.2.1.2 Analysis of the Key Secondary Estimand**

The key secondary analysis of progression to severe disease or death will be a logistic regression model.

Covariates will be included in the logistic regression model as per [Section 7.2](#).

The number and percentage of patient with severe disease or who died within each treatment group will be presented with the difference in the proportions of patients with severe disease or who died between the treatment groups. The difference in proportions will be calculated using the methods proposed by Ge et al [9]. In addition, the odds ratio, the 95% CI for the odds ratio and the associated p-value will be displayed.

If quasi-complete separation of a covariate occurs the Firth logistic regression method will be used to avoid using maximum likelihood estimation when calculating the estimates.

The Hochberg procedure used in the primary analysis will dictate whether the statistical significance of the key secondary analysis of progression to severe disease or death will be formally assessed, as detailed in [Section 7.6](#) and a statistically significant p-value according to the multiple testing strategy will be indicated in the output.

The odds ratios for severe disease or death, intubation or death and death in SNG001 versus placebo and their corresponding 95% CI and p-values will be presented in a forest plot, in which the x-axis will represent the odds ratios and the y-axis will stand for the estimates of the three key secondary endpoints.

#### **9.2.1.3 Sensitivity Analyses of the Key Secondary Estimand**

The sensitivity of the key secondary analysis to missing data due to withdrawal from study prior to progression to severe disease or death will be assessed firstly through a tipping point analysis for a range of sensitivity parameters,  $\delta_i$ , for each  $i^{\text{th}}$  patient.  $\delta_i$  represents the change to the odds of severe disease or death. If  $\delta_i$  is set to 1 this will represent a Missing at Random (MAR) approach, if  $\delta_i < 1$  the imputed OSCi score will be lower than that of the MAR approach and progression to severe disease will be less common. If  $\delta_i > 1$  the imputed OSCi score will be higher than that of the MAR approach and progression to severe disease will be more common. Values of  $\delta$  will be varied independently for each treatment group.

Missing data will be imputed in M datasets. OSCi will be considered a categorical variable and the imputation algorithm will use a monotone logistic regression method to impute missing OSCi scores. Each of the covariates used in the primary analysis, including treatment group, will be included as covariates in the logistic regression. Missing data will be imputed iteratively by day, starting at day 2. For each subsequent day, the OSCi scores at prior days will be included as covariates, including the OSCi scores imputed in earlier iterations. This will not include the OSCi score at day 1 because this will always be 4, by design. However, because there are 34 scheduled visit days to be imputed in this way it is likely as the imputation progresses that the imputation model will become over-parameterised. To avoid this issue and to account for the fact that the most recent days are most likely to be predictive, only the OSCi score at the previous two days will be used as continuous covariates. Any imputations of 8 (death) will be “carried forward” to all future missing days after each step and not imputed again.

For each imputed dataset and for each value of  $\delta_i$  the primary analysis method will be repeated. The estimates from the imputed datasets will be combined for each value of  $\delta_i$  using Rubin’s rules. The results for the different combinations of  $\delta_i$  for Placebo and SNG001 patients will be plotted on a heat map to identify, if applicable, where the p-values becomes insignificant. This ‘tipping point’ will also be tabulated along with specific values of  $\delta_i$ .

A second sensitivity of the primary analysis to missing data will follow the jump to reference MNAR method of imputation detailed in [Section 9.1.1.3](#). The key secondary analysis model will be repeated for each imputed dataset and the combined estimates, as calculated by Rubin’s rules will be tabulated.

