**Table 8: Intercurrent events and policies for the primary estimand of time to hospital discharge**

Intercurrent event	Policy
Death	Composite variable: Patients who die on or prior to Day 28 will have time to hospital discharge right censored at 28 days (the maximum time to discharge).
Premature treatment discontinuation and missed doses	Treatment policy: The time to hospital discharge will be used regardless of treatment discontinuation and the number of missed doses.
Withdrawal from study following hospital discharge	Hypothetical: The time to hospital discharge will be used regardless of study withdrawal where discharge was sustained for 7 days. Otherwise, patients will be censored at the last date known to be hospitalised for patients who withdrew during the 7 day rebound period. This approach has been proposed because discontinuation during the rebound period is expected to be due to lack of interest/lack

	of motivation/lack of time to continue participating in the study rather than relapse.
Withdrawal from study prior to hospital discharge	While-on-study: Time to hospital discharge will be right censored at the time of withdrawal from the study or at 28 days, whichever occurs first. The evaluation period for this endpoint is 28 days, therefore estimating the time to hospital discharge after Day 28 would not be appropriate. Premature study withdrawal is expected to be independent to the treatment effect, therefore a censoring approach in this scenario is considered appropriate. However, this assumption will be tested by appropriate sensitivity analyses.
Other protocol deviations and concomitant medications affecting efficacy	Treatment policy: Time to hospital discharge will be used regardless of any concomitant medication use or protocol deviations.

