## Statistical Analysis Plan (RotW)

Final v1.0, 08FEB2022

SG018

as described by Jackson et al [6]. To perform the multiple imputation M datasets will first be created through bootstrapping. The bootstrapping will be applied independently for each treatment group (a treatment stratified bootstrap). Each created dataset will therefore contain  $n_1$  Placebo patients and  $n_2$  SNG001 patients where  $n_1$  and  $n_2$  are the number of patients randomised to Placebo and SNG001 respectively. The primary analysis method will be used to assess each of the bootstrapped datasets to generate estimates of the model coefficients within each dataset. The vector of model coefficients can be written algebraically for the  $j^{\text{th}}$  dataset as  $\beta_j^*$  and the vector of covariates values for the  $i^{\text{th}}$  patient as  $Z_i$ .

Missing hospital discharge and recovery times for patients censored prior to day 28 will be estimated as  $\min(T_{ij} = C_i + A_{ij}, 28)$ , where  $T_{ij}$  is the imputed time to discharge/recovery in the  $j^{\text{th}}$  dataset for the  $i^{\text{th}}$  patient,  $C_i$  is the observed censored time and  $A_{ij}$  is the simulated time between censoring and the time to event. A maximum constraint of 28 days is applied to the imputed times because the rate and time to hospital discharge and recovery beyond this time cannot be assessed due to the limitations of the study design.  $A_{ij}$  will be estimated using the Bender et al method [7], by the following calculation:

$$A_{ij} = H_{A_{ij}}^{-1}[-\log(U_{ij})\exp(-\beta_j^*Z_i - \gamma_i)],$$

where  $U_{ij}$  is randomly generated from a Uniform(0,1) distribution,  $H_{A_{ij}}^{-1}$  is the inverse cumulative baseline hazard function for  $A_{ij}$  and  $\gamma_i$  is a sensitivity parameter. If  $\gamma_i$  is set to 0 this will represent a Missing at Random (MAR) approach, if  $\gamma_i < 0$  the time to discharge/recovery will occur earlier than that of the MAR approach and if  $\gamma_i > 0$  discharge/recovery will occur later than that of the MAR approach. Values of  $\gamma$  will be varied independently for each treatment group.

The M imputed datasets will be analysed using the primary analysis model and the M estimates will be combined with Rubin's variance formula.

The value of M will be chosen large enough such that the choice of the seed used in sampling functions has a negligible impact on estimates.

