For each imputed dataset and for each value of  $\gamma_i$  the primary analysis method will be repeated. The estimates from the imputed datasets will be combined for each value of  $\gamma_i$  using Rubin's rules [8]. The results for the different combinations of  $\gamma_i$  for Placebo and SNG001 patients will be plotted on a heat map to identify, if applicable, where the p-values becomes non-significant. This 'tipping point' will also be tabulated along with specific values of  $\gamma_i$  on the exponentiated scale.

A jump to reference Missing Not at Random (MNAR) data imputation will also be performed using similar a method, but only assuming all patients who withdraw early follow the same pattern as patients who are randomised to placebo.  $\gamma_i$  will be set to 0 for this imputation.

These sensitivity analyses will assess the robustness of the results to a departure from the censored at random assumption of a Cox proportional hazards model. To aid interpretation the average proportion of patients who were discharged from hospital will be presented alongside the average difference in the restricted mean survival time.

An additional sensitivity analysis will assess hospital discharge that has been sustained for 7 days. In this analysis patients will be considered as discharged from hospital if they are not re-admitted to hospital within 7 days of hospital discharge. This analysis will evaluate the the primary endpoint using the same rebound assessment period for all patients .

The primary estimand will be further evaluated for each of the subgroups described in [Section 7.2](#). The analysis method for the primary endpoint described in [Section 9.1.1.2](#) will be used to evaluate each subgroup.

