## Statistical Analysis Plan (RotW)

Final v1.0, 08FEB2022

SG018

The above sensitivity analyses represent a change to the handling of the intercurrent event 'Withdrawal from study' to a treatment policy.

A third sensitivity analysis will be performed on the subset of patients who have completed Day 35 or who have died prior to Day 35. Patients who did not withdraw prior to Day 35 and who have at least 1 completed assessment between Day 31 and Day 35 will be considered completers. This is to exclude patients who are lost to follow-up during the first 35 days of the study but are re-contacted at a later date. The key secondary analysis model will be repeated for this subset.

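### The jump-to-reference analysis of the key secondary endpoints points to a method that imputes discharge and recovery times to Day 28, so as written it cannot supply severe disease, intubation or death to Day 35

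*SAP*

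**What the plan says.** **Key secondary endpoints.** SAP 5.3.1.3 to 5.3.1.5 define three yes/no outcomes: OSCI of 5 or more, OSCI of 6 or more, and death, each at any time up to and including Day 35. The main analysis (9.2.1.2) is a logistic regression. It uses available data, so progression counts only if it is seen before withdrawal (7.3.1.3).

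**Sensitivity analyses in SAP 9.2.1.3.** There are three for missing data.

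1. A tipping-point analysis, which imputes OSCI scores day by day with a monotone logistic model that has treatment group among its covariates.
2. A jump-to-reference analysis: "A second sensitivity of the primary analysis to missing data will follow the jump to reference MNAR method of imputation detailed in" Section 9.1.1.3. The text goes on: "The key secondary analysis model will be repeated for each imputed dataset".
3. A completer analysis.

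Of the first two the SAP says: "The above sensitivity analyses represent a change to the handling of the intercurrent event 'Withdrawal from study' to a treatment policy". Sections 9.2.2.3 and 9.2.3.3 apply the same approach to intubation or death and to death.

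**The method referred to.** SAP 9.1.1.3 reads: "Missing hospital discharge and recovery times for patients censored prior to day 28 will be estimated as" min(C + A, 28), where C is the censoring time and A is a draw based on the fitted Cox model. It adds: "A maximum constraint of 28 days is applied to the imputed times". Jump-to-reference is introduced there as a variant: "A jump to reference Missing Not at Random (MNAR) data imputation will also be performed using similar a method", "only assuming all patients who withdraw early follow the same pattern as patients who are randomised to placebo", with the sensitivity parameter set to 0.

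**The protocol.** Section 8.4.2 calls for severe disease itself to be imputed under a missing-not-at-random approach. Section 8.5.5 describes that approach, for selected analyses, as an imputation model estimated from the placebo group, and leaves the details to the SAP.

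**The concern.** The cross-reference leads to an algorithm built for a different outcome. The key secondary model needs a yes/no answer on progression or death by Day 35 for each patient. Section 9.1.1.3 returns a discharge or recovery time of at most 28 days. A programmer following the text would reach a dataset with nothing new in it for the logistic model to use, and would have to devise an imputation.

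These endpoints are in the formal testing sequence (SAP 7.6), and the main analysis in effect counts withdrawn patients as not progressing after they leave. A reference-based check is one of the ways the plan tests that assumption. If its algorithm is chosen after unblinding, it loses much of its value as a prespecified check.

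**Working it through.** **The plan's own figure.** SAP 9.2.1.3 says its OSCI imputation covers 34 scheduled days, starting at Day 2. Day 2 to Day 35 inclusive is 35 − 2 + 1 = 34, which agrees. That algorithm therefore reaches the key secondary horizon.

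**What is needed against what Section 9.1.1.3 gives.**

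| | Key secondary model needs | Section 9.1.1.3 gives |
|---|---|---|
| Variable | OSCI of 5 or more, OSCI of 6 or more, or death | Time to discharge or recovery |
| Horizon | Day 35 | min(C + A, 28), so at most Day 28; the last 35 − 28 = 7 days are not covered |
| Patients | All who withdraw before Day 35 without a recorded event | Those censored before Day 28 without discharge or recovery |
| Death | Part of all three outcomes | Not modelled: "Patients who die on or prior to Day 28 will have time to hospital discharge right censored at 28 days" (SAP Table 8) |

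The first row is enough to settle the matter. A discharge time, or its absence, does not say whether a patient needed non-invasive ventilation or intubation, or died. The jump-to-reference paragraph of 9.1.1.3 changes only whose hazard is used; it adds no OSCI draw.

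**How many patients the analysis is meant to address.** SAP Section 6 assumes 25% withdraw before Day 35: 0.25 × 610 = 152.5, about 153.

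**How many of these Section 9.1.1.3 would touch at all.** This is an illustration. It assumes the SAP placebo rates in both arms, the SAP withdrawal model (all withdrawals by Day 28) and independence.

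- Withdrawal rate: λw = ln(100/75)/28 = 0.01027 per day.
- Discharge rate: λd = ln(100/30)/28 = 0.04300 per day.
- Recovery rate: λr = ln(100/70)/28 = 0.01274 per day.

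The probability of withdrawing before discharge and before Day 28 is λw/(λw + λd) × (1 − 0.75 × 0.30) = 0.1929 × 0.775 = 0.1495, or 0.1495 × 610 ≈ 91 patients. The other 152.5 − 91.2 ≈ 61 withdraw after discharge and get no imputed value. A simulation with the same inputs also gave about 91.

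The SAP treats withdrawal within 7 days of discharge as not discharged. With that rule the group already counted as discharged is λd/(λd + λw) × e^(−7λw) × (1 − e^(−21(λd + λw))) − 0.75 × (1 − e^(−21λd)) = 0.8071 × 0.9306 × 0.6733 − 0.75 × 0.5946 = 0.0598, or about 36 patients.

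On the recovery clock, ignoring the 7-day rule, the imputed group is 0.4465 × (1 − 0.75 × 0.70) = 0.4465 × 0.475 = 0.2121, or about 129, leaving about 23.

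So roughly 23 to 61 of the 153 would be skipped, depending on which clock is used and how the 7-day rule applies. The SAP does not say which clock to use. For those it does reach, the imputed value is still not a key secondary outcome.

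**The case against.** The best defence is that only the principle is borrowed. Jump-to-reference means that withdrawn patients behave like placebo patients. The sentence directly follows the Day 2 to Day 35 OSCI imputation, the model to be fitted needs a progression outcome, and the protocol asks for severe disease to be imputed from a placebo-based model. The 28-day cap is justified in the SAP for discharge and recovery only.

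This is probably what was meant, and it points to the right repair. It does not cure the text. The SAP cites the method of imputation in 9.1.1.3, not the OSCI method just above. That OSCI method keeps treatment group as a covariate and has no placebo-reference version, so how treatment enters is left open.

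The defence is right that the consequence is small. The tipping-point analysis departs from missing at random whenever its parameter differs from 1, varies it by arm, and runs to Day 35. The completer analysis is also intact.

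A reader might draw three stronger conclusions, none of which the documents support.

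- *That the analysis would turn every patient withdrawn before Day 28 into an event, adding up to 25 percentage points.* This requires the imputed time to be read as time to progression and values at the cap to be coded as events. The SAP states neither, and elsewhere treats Day 28 as a censoring point (Table 8; Section 6).
- *That it would simply reproduce the main analysis.* The SAP says withdrawal is handled here by treatment policy, so imputing nothing is not the intended reading.
- *That about 30% withdraw by Day 35, with some 5% leaving after Day 28.* That extends the withdrawal rate beyond the SAP's own cap at Day 28. Section 6 puts withdrawal before Day 35 at 25%, with the other 75% fully followed.

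**Conclusion.** The concern holds. The stated rule is wrong for these endpoints, not merely brief: Section 9.1.1.3 has the wrong variable, horizon and patient set. As written it cannot deliver the imputation that protocol 8.4.2 requires for severe disease, or the treatment-policy handling that the SAP claims for it.

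The defect affects one of three missing-data sensitivity analyses, for each of the three key secondary endpoints. It does not touch the main estimates, the other two sensitivity analyses, the testing sequence or the sample size. No numerical bias can be given, because the method yields no key secondary result to compare. The conclusion rests on the wording of the two SAP sections; the patient counts are illustrative and rest on the Section 6 rates.

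**What to change.** In SAP 9.2.1.3, replace the cross-reference to 9.1.1.3 with wording such as:

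> Missing OSCI scores after withdrawal will be imputed day by day to Day 35 with the monotone logistic method of this section. The imputation model will be estimated from placebo patients only, without a treatment term, and applied to withdrawn patients in both arms, with delta = 1. The key secondary model will then be fitted to each dataset and the estimates combined by Rubin's rules.

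This follows protocol 8.5.5 and settles how treatment enters the model. Sections 9.2.2.3 and 9.2.3.3 then inherit it unchanged, since imputed scores of 6 or more and of 8 give the other two outcomes.

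The cost is a SAP wording change before unblinding and a modest adaptation of the OSCI imputation program already planned for the tipping-point analysis. No new data are needed.
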